#### **3.4 Subject Selection**

The Principal Investigator at each center has the responsibility of screening potential candidates to determine if they meet all the entry criteria. Subjects receiving new ICDs and at high-risk of ICD therapy are to be included. Those subjects receiving new ICDs (within 90 days of the study enrollment) for standard clinical reasons who also have documented MMVT will be considered for inclusion. MMVT may be evidenced using an EP study or Non-Invasive Programmed Stimulation study (NIPS) unless documented

spontaneous MMVT is available. Subjects who refuse ICD and undergo ablation will be included in a prospective registry arm.

### 3.4.1 Inclusion Criteria

- Patient is receiving a new ICD or CRT-D implant that has study required programming capabilities and is appropriate for remote monitoring. Patient who has received the ICD / CRT-D within 90 days of enrollment can also be enrolled.
- Patient who has a high risk of ICD shock as shown by documented Monomorphic VT (MMVT) by one or more of the following:
  - Spontaneous MMVT
  - Inducible MMVT during EP Study,
  - Inducible MMVT during NIPS Study

\*Inducible MMVT is defined as MMVT > 30 seconds or requiring electrical termination (ATP or cardioversion)

- Patient has EF < 50% or RV dysfunction
- Patient has a cardiomyopathy with structural heart disease of any cause
- 18 years of age or older
- Patient has been informed of the nature of the study and has agreed to its provisions and provided written informed consent approved by the Institutional Review Board.

### 3.4.2 Exclusion Criteria

- Any history of debilitating stroke with neurologic deficit
- ST elevation MI or previous cardiac surgery within 60 days prior to enrollment
- Patient is pregnant or nursing
- Patient has chronic NYHA class IV heart failure
- Patient has incessant VT necessitating immediate treatment
- Patient has VT/VF thought to be from channelopathies
- Limited life expectancy (less than one year)
- Patient has current class IV angina
- Recent CABG or PCI (< 45 days)
- Patient is currently participating in another investigational drug or device study
- Patient is unable or unwilling to cooperate with the study procedures
- Known presence of intracardiac thrombi
- Prosthetic mitral or aortic valve or mitral or aortic valvular heart disease requiring immediate surgical intervention
- Major contraindication to anticoagulation therapy or coagulation disorder
- Left Ventricular Ejection Fraction < 15%
- Patient has had a previous ablation procedure for VT, excluding remote (> 3 months) outflow tract tachycardia
- Patient has GFR < 30 mL/min/1.73m^2

- Patient has peripheral vascular disease that precludes LV access
- Patient is thought to have idiopathic outflow VT as only VT
- Patient has a PVC or VT induced cardiomyopathy that is expected to resolve with ablation and will not require an ICD
- Patient has reversible cause of VT
- Patient does not meet criteria for ICD or CRT-D

### **3.5 Study Design Overview**

[figure not shown]
Based on assumptions from the SMASH VT trial and the AVID study, a 50% reduction in events from ablation is projected with a 50% event rate in the control arm at 2 years. 120 patients are required to achieve 80% power to detect a true difference of this magnitude with a two-sided alpha error of 0.05. The primary endpoint is a composite that includes cardiovascular rehospitalization and death, which will increase event rates at an estimated 10%/year, individually.(1,4)

#### **3.5.1 Randomization**

Subjects who meet inclusion/exclusion criteria will be entered into the randomized trial. Randomization will be 1:1 between control group and ablation group. Those randomized to the control group will receive ICD therapy and routine drug therapy (including antiarrhythmic drugs as indicated). Subjects randomized to the ablation group will receive ablation therapy plus ICD for ventricular tachycardia. Patients that refuse ICD therapy and undergo ablation only will be enrolled in a prospective registry. All primary statistical analyses will be performed on an intent-to-treat basis.

Central randomization is conducted by the coordinating site. Prior to 10/12/16, the participating sites performed randomization using a table (block size of 4) provided by the coordinating site. After additional in-house statistical review of the protocol, electronic randomization from the coordinating site was advised. Central electronic randomization commenced on 10/12/2016. 25 patients were enrolled using the original randomization table schema. The remaining patients were randomized using electronic randomization.

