#### **3.3 Clinical Centers**

We anticipate enrollment of 120 patients for this pilot study at 8-12 institutions with extensive experience in complex ablation procedures. As a conservative estimate, enrollment will occur over a 2 year period, with 60 patients per year (7-8 patients/year at each institution). Additional centers may be considered based on clinical competency and experience.

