### 3.6 Study Population

#### 3.6.1 Randomized Subjects

The **Intent to Treat (ITT)** population includes all randomized subjects. These subjects can be included in the randomized trial if they meet all other entry criteria.

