### **9.3 Primary Endpoint Analysis**

The primary endpoint analysis will be a time to event analysis and account for censored observations for all randomized subjects. Intention to treat analysis will be used for this endpoint; the analysis will be “analyzed as randomized” regardless of the actual treatment patients receive during the follow-up period. Kaplan-Meier (1958) estimates of the primary endpoint and overall survival will be generated along with 95% confidence intervals for the median time to event or death (Brookmeyer and Crowley, 1982).(8,9) Log-rank test will be used to compare the hazard functions between the two groups. Cox (1972) regression models will be fit to assess and adjust for baseline covariates.(10) The median time to VT recurrence as well as the 95% confidence intervals will be reported for both groups. The event free survival probability as well as the 95% confidence intervals at the 24-month follow-up for both groups will be presented. Adverse events will be tabulated by type and level of severity and compared between groups using chi-square or Fisher exact tests.

Secondary analyses comparing outcomes in the ICD+ablation and ICD arms vs. the registry patients (ablation only) will be performed in a similar manner to those described above.

Interim analyses will be generated by the coordinating center annually. A Peto-Haybittle efficacy monitoring boundary will be used: if the p-value for the difference between groups is <0.001, early stopping of the trial will be considered. Using this monitoring bound, the p-value for statistical significance at the final analysis will remain at the nominal 0.05 level.

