## **10. MONITORING**

Each participating center is responsible for study execution, data collection and monitoring for protocol compliance and conduct. The coordinating site may be consulted regarding any questions specific to protocol conduct.

The coordinating site will collect a copy of the IRB/EC approval letter for each site, as well as a copy of the final approved informed consent before randomization can begin. The coordinating site will collect a final complete data set from each site, and may work with the sites regarding any questions or outstanding data elements.

Upon inspection of the final data set, the coordinating site may request to see source documentation, reports of protocol deviations or adverse events if needed to verify data elements.

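### Do the 25 patients allocated from a site table before central randomization call for a planned sensitivity analysis without them?

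*Combined protocol and SAP*

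**What the plan says.** Section 3.5.1 describes two allocation methods. Before 10/12/2016, "the participating sites performed randomization using a table (block size of 4) provided by the coordinating site". The change is explained by "After additional in-house statistical review of the protocol, electronic randomization from the coordinating site was advised", and the number affected is given: "25 patients were enrolled using the original randomization table schema". Everyone after that date was allocated electronically from the coordinating site. The section does not say how the table was concealed, whether each site had its own, what the statistical review found, or what blocking or stratification the electronic system used.

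On analysis, Section 3.6.1 states that the intention-to-treat "population includes all randomized subjects", and Section 9.3 says "Intention to treat analysis will be used for this endpoint". Section 9.3 adds that Cox "regression models will be fit to assess and adjust for baseline covariates", without naming the covariates. The only subgroup named in Section 9.2 is RV cardiomyopathy. Neither section splits results by allocation method or period.

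Section 3.3 gives the planned scale: "We anticipate enrollment of 120 patients for this pilot study at 8-12 institutions". Section 10 leaves monitoring to each center and says that, at the stage of reviewing completed data, "the coordinating site may request to see source documentation, reports of protocol deviations or adverse events if needed to verify data elements".

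**The concern.** The arms are ICD plus ablation against ICD with drug therapy, no blinding is described, and for about a fifth of the planned patients the sites worked from the allocation table themselves. Staff who know the block size and the earlier assignments can often predict the next one. Staff who can read the table know it outright. Either would let them influence who is enrolled and when, and intention-to-treat analysis does not undo that. Cox adjustment corrects only measured imbalance, and the source check in Section 10 is optional and comes after the event.

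The coordinating site changed the method on statistical advice, yet the analysis plan does nothing separate with the 25 patients already allocated. An obvious response is a supportive log-rank and Cox analysis in the centrally randomized patients, offered as an estimate free of the site-table risk.

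**Working it through.** **Inputs.** 120 patients, 60 per arm, 50% control events at 2 years, halved by ablation, two-sided alpha 0.05 (Sections 1 and 9.1); 25 patients from the table, block size 4, 1:1 (3.5.1); 8-12 sites (3.3). The final randomized number is not given. Assumptions: one table per site, an even spread of the 25, and patients who can be steered between hazards differing k-fold.

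**1. Plan's own figure.** For 50% against 25% with n = 60 per arm and pooled rate 0.375:
- SE under the null = sqrt(2 × 0.375 × 0.625/60) = 0.0884
- SE under the alternative = sqrt((0.25 + 0.1875)/60) = 0.0854
- Power = Φ((0.25 − 1.96 × 0.0884)/0.0854) = Φ(0.90) = 81.6%, consistent with the stated 80%.

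**2. Predictability of a block of 4.** Guess the arm with fewer assignments so far in the block, and do not guess when tied. The second position always allows a guess, right 2/3 of the time. The third allows one in 1/3 of blocks, always right. The fourth is certain.
- 12 sites (eleven with 2 patients, one with 3): 12 + 1/3 = 12.33 guesses; 12 × 2/3 + 1/3 = 8.33 correct.
- 8 sites (seven with 3, one with 4): 8 + 8/3 + 1 = 11.67 guesses; 16/3 + 8/3 + 1 = 9.00 correct.
- 3 sites (8, 8 and 9): six full blocks, each with 2 correct and 1/3 wrong on average, so 12 correct and 2 wrong.

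**3. Effect on the pooled result with no true treatment effect.** Each guess moves the log hazard by ½ ln k, so in the 25, ln HR ≈ −[(correct − wrong)/25] × ln k. The pooled z-statistic shifts by (25/120) × |ln HR| × sqrt(60/4), with 60 events expected under no effect. The false-win chance is 1 − Φ(1.96 − shift).

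| Active sites | (correct − wrong)/25 | HR in the 25, k = 2 / 4 | False win, k = 2 / 4 |
|---|---|---|---|
| 12 | 4.33/25 = 0.173 | 0.89 / 0.79 | 3.1% / 3.9% |
| 8 | 6.33/25 = 0.253 | 0.84 / 0.70 | 3.4% / 4.7% |
| 3 | 10/25 = 0.400 | 0.76 / 0.57 | 4.1% / 6.5% |

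Simulation with 20,000 trials per setting gives 3.3% / 3.9% at 12 sites and 3.4% / 4.5% at 8. For three sites simulation gives about 4% / 6%. If the table could be read in full and all 25 were steered, simulation gives 7.7% / 18.5%. The unbiased level is 2.5%.

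**4. Would the later 95 be cleaner?** Against reading ahead in a table, yes. Against guessing, only if electronic allocation was unpredictable. Suppose it kept site blocks of 4, an assumption on which the documents are silent. Full blocks give (2 − 1/3)/4 = 0.417, so for k = 2 ln HR = −0.417 × 0.693 = −0.289. With 47.5 events the shift is 0.289 × sqrt(47.5)/2 = 0.995, and the false-win chance in the 95 alone is 1 − Φ(0.965) ≈ 17%. For k = 4 simulation gives about 47%. On that assumption the restricted set is worse than the pooled one.

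**5. What the extra analysis could show.**
- Power with 47.5 per arm: Φ((0.25 − 1.96 × 0.0993)/0.0960) = 71.8%. By log-rank, 95 × 0.375 = 35.6 events and HR = ln 0.75/ln 0.5 = 0.415 give 74.7%.
- Expected 95% CI, 0.415 × exp(±1.96 × 2/sqrt(events)): 0.22-0.80 at 35.6 events, against 0.23-0.74 at 120 × 0.375 = 45.
- The two estimates share 95 patients. With no effect, the SD of the difference in log HR is sqrt(4/47.5 − 4/60) = 0.132, so chance alone moves the ratio of pooled to central HR over exp(±1.96 × 0.132) = 0.77 to 1.30. Under the planned effect the SD is sqrt(4/35.6 − 4/45) = 0.153, giving 0.74 to 1.35.
- The simulated 8 and 12 site scenarios move that ratio only to 0.93-0.98 and fall outside the no-effect limits 5-8% of the time, against 5% with no bias.

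**The case for a change.** The best case for adding the analysis is that it is nearly free. The switch date and the number affected are on record, it repeats analyses already planned, and the primary analysis would stay as it is. The coordinating site itself moved to central allocation, so reporting the result under that method seems natural. A readable table, which the documents neither show nor exclude, would matter far more than guessing. Section 1 states that no analysis had been done as of 28 April 2020, so at that date the addition could still have been made before results were seen.

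Much of this stands. The risk is real in principle, nothing in Section 9.3 or Section 10 removes it, and a reader may reasonably want to see the later patients on their own. What does not stand is the step from there to a needed change. The restricted estimate is protected against reading ahead in a table. It is not protected against block guessing unless the electronic scheme was unpredictable. Similar hazard ratios would not clear the 25 patients, and differing ones could reflect chance, site mix or operator experience.

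**Conclusion.** No change to the plan is needed. The facts are as stated: 25 patients, 20.8% of the planned 120, were allocated by sites from a block-of-4 table whose concealment is not described. That is a possible source of selection bias, not a demonstrated one. The plan discloses the method, the date of the switch and the number affected, allocation was moved to the center, and the pooled intention-to-treat analysis is the correct primary analysis.

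Under deliberate guessing at every opportunity, the false-win chance rises from 2.5% to about 3.1-4.8% at 8 to 12 active sites and about 4-6% at three. These figures rest on one table per site, an even spread of the 25, and 2-fold to 4-fold hazard differences open to steering. The number of sites active before the switch is not given, and fewer sites mean more inflation. A false-win rate of about 2.5% in the later 95 holds only if electronic allocation could not be predicted.

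A supportive analysis in those 95, with about 72-75% power, is an optional extra that analysts may report. It would leave the primary result unchanged and could neither confirm nor rule out bias, so its absence is not a defect.

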### 3.6 Study Population

#### 3.6.1 Randomized Subjects

The **Intent to Treat (ITT)** population includes all randomized subjects. These subjects can be included in the randomized trial if they meet all other entry criteria.

#### 3.6.2 Registry Subjects

Patients that refuse ICD implantation will not be randomized and will be approached to sign consent for inclusion into a registry if they undergo catheter ablation without ICD. Basic demographics and medical history will be collected from registry subjects upon enrollment. Registry subjects will receive a phone contact and follow-up with clinic visits and device interrogation at 3, 6, 12, 18, 24, 30 and 36 months to check on their overall status. Due to the COVID19 global pandemic, China centers were shut down and complete access for patient follow-up will require an additional 6-12 months. Therefore, we are requesting one extra year extension for follow up due to these unanticipated circumstances. No statistical review or analysis was performed,

as follow-up remains incomplete as of April, 28th, 2020. Registry subjects will receive a phone contact and follow-up with clinic visits 30 and 36 months to check on their overall status

### **3.6.3 Discontinued Subjects**

- Lost to follow-up: subjects may be lost to follow-up despite exhaustive attempts to contact them. A minimum of two (2) attempts (by telephone or mail) to contact such subjects will be made and then a certified letter will be sent to the last known address. Attempts to contact the subject will be documented.
- Subject/Family request: subjects may voluntarily decide to withdraw from the study with no penalty. If a subject chooses to discontinue participation in the study at the time of a study visit, the required assessments for that visit will be completed. If the subject notifies the clinical center by mail or phone, he/she may be requested to come in to have a final assessment.
- Subject's participation terminated by Investigator: a subject's participation may be discontinued if the Investigator considers that it is in the subject's best interest.
- Subject's participation terminated by site PI request.
- Subject Death.

If a patient is discontinued from the study, the reason for discontinuation will be documented and the data collected from this subject will be used in the final analysis and treated as censored subject.

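### Investigators and site PIs can end a subject's participation, after which the subject is censored with no further endpoint follow-up; this permits informative censoring in the primary log-rank analysis

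*Combined protocol and SAP*

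**What the plan says.** Section 3.6.3 lists the ways a subject can leave the study: loss to follow-up, request of the subject or family, termination by the investigator, termination by the site PI, and death. The investigator's route has a criterion: "a subject's participation may be discontinued if the Investigator considers that it is in the subject's best interest". The site PI's route has none: "Subject's participation terminated by site PI request".

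One rule covers the whole list. For the analysis it says that "the data collected from this subject will be used in the final analysis and treated as censored subject". It also requires a record of why the subject left. A final assessment is mentioned only for subjects who withdraw themselves. Nothing is said about collecting endpoints or vital status after any discontinuation. The last item on the list is "Subject Death".

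On the analysis side, section 3.6.1 says that the intention-to-treat "population includes all randomized subjects". Section 9.3 states that "The primary endpoint analysis will be a time to event analysis and account for censored observations for all randomized subjects", with subjects analysed as randomized "regardless of the actual treatment patients receive during the follow-up period". The methods are Kaplan-Meier estimates, a log-rank test and Cox models. No sensitivity analysis for censoring is described.

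**The concern.** Kaplan-Meier and log-rank methods are valid only if, within each arm, a subject who is censored has the same future risk as those still followed. Discontinuation decided by the site is where that assumption is weakest. An exit in the subject's best interest is prompted by the subject's condition, and an exit at the PI's request can be prompted by anything.

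The setting adds to the exposure. Blinding is not mentioned anywhere, and one arm has an invasive procedure performed at the site, so it is a sound inference that site staff know the arm. Under sections 4.9 and 10 the sites monitor their own data and conduct, and no endpoint committee is described.

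If subjects who are about to have an event are censored more often in one arm, that arm looks better than it is. If this happens in the ablation arm, the false-positive rate rises. If it happens in the control arm, a real benefit is diluted. The data in hand cannot show which has occurred, because the outcomes that would show it were never collected.

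The same section has a second fault that needs no assumption about behaviour. Death is on the list of discontinuations to be censored, while sections 3.2 and 9.2 make all-cause mortality a component of the primary endpoint.

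**Working it through.** **Inputs.** From sections 3.5.1, 3.5 and 9.1: 1:1 allocation, 120 subjects (60 per arm), a 50% control event rate at 2 years, a 50% reduction (so 25% with ablation), 80% power, two-sided alpha 0.05. From section 9.3: the log-rank test. From section 9.2: 2 years of follow-up. The documents do not give a discontinuation rate, its split by arm, or its relation to risk. These are assumed below and shown over a range.

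**The plan's own figure.** Two proportions, per arm:

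n = [1.96·√(2·0.375·0.625) + 0.842·√(0.25 + 0.1875)]² / 0.25² = (1.342 + 0.557)² / 0.0625 ≈ 58

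That is 116 in total, and power with 60 per arm is 81.6%. As a time-to-event design, HR = ln 0.75 / ln 0.50 = 0.415. Freedman's formula gives 46 events, and 46 / 0.375 ≈ 123 subjects. The planned 120 is therefore reproduced to within rounding and is not in dispute. It leaves almost no room for censoring: 116 / 0.97 ≈ 120 covers 3% loss, and 10% loss would need 116 / 0.90 ≈ 129.

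**Set-up of the illustration.** Exponential event times, 60 per arm, administrative censoring at 24 months, control hazard ln 2 / 24 per month (50% events), log-rank test at |Z| > 1.96, 20,000 simulated trials per cell. Selective censoring means that a share of would-be events in one arm is recorded as censored just before the event. At a 50% event rate, 30 events are expected per arm, so 10% is about 3 subjects.

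**No true effect, selective censoring in the ablation arm only:**

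| Ablation events censored | Apparent HR | Two-sided rejection |
|---|---|---|
| none | 1.00 | about 5% |
| 10% (about 3) | 0.90 | about 7% |
| exactly 5 | 0.83 | about 11% |
| 20% (about 6) | 0.80 | about 13% |
| 30% (about 9) | 0.70 | about 24% |

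**Planned effect (HR 0.415), selective censoring in the control arm only:**

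| Control events censored | Apparent HR | Power |
|---|---|---|
| none | 0.42 | about 82% |
| 10% (about 3) | 0.46 | about 70% |
| 20% (about 6) | 0.52 | about 53% |
| 30% (about 9) | 0.59 | about 35% |

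A second run with a different random seed agreed to within about one percentage point.

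**The case against.** The strongest reply is that this is ordinary protocol text. Withdrawal in the subject's best interest protects participants, the reason must be recorded so exits can be audited, and section 9.3 already says that censoring will be accounted for. The documents do not show that anyone would use these routes selectively. All of that is fair, and it limits the point to a possible bias. It does not remove the point: a recorded reason does not recover an unobserved outcome, accounting for censoring by log-rank presumes that it is uninformative, and the PI route has no criterion to audit against.

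Three stronger readings are tempting, and the documents do not support them.

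- A reader might infer that the rule breaks the intention-to-treat analysis. It does not. All randomized subjects stay in their assigned arm and their data to discontinuation are used. Nothing says that stopping or changing treatment triggers censoring.
- A reader might take the projected 30 versus 15 events (uncorrected chi-square p = 0.005), note that 30 versus 20 gives p = 0.064, and infer that five censored ablation subjects are enough to create a false positive. But 30 versus 20 is 50% versus 33%, a real one-third reduction. The chi-square also counts censored subjects as event-free to 24 months and is not the planned test. Under a true null with the log-rank test, five such subjects give about 11% rejection, so about 89% of such trials would remain non-significant.
- A reader might infer that section 3.6.3 certainly ends observation, not only treatment. That is the natural reading of ending participation with censoring, but the text does not spell it out. The ambiguity is itself a reason to reword.

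**Conclusion.** The point holds as a weakness in follow-up and in the censoring assumption, not as a failure of intention-to-treat. Section 3.6.3 permits arm-aware site staff to end a subject's participation, in one case without any criterion, and censors the subject with no later outcome collection. Section 9.3 then relies on censoring being unrelated to risk and has no check on it.

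In a trial of 120, a handful of selective exits could matter: two-sided error of roughly 7% to 24% for about 3 to 9 hidden ablation-arm events, or power down to roughly 70% to 35% for the same shares of control-arm events. These figures assume exponential times, exits confined to one arm, and censoring immediately before the event. That is a deliberately adverse pattern, so they illustrate sensitivity and do not predict bias. Neither the direction nor the actual size can be derived from the documents.

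The treatment of death is a direct contradiction between section 3.6.3 and sections 3.2 and 9.2, and must be reconciled whatever view is taken of the rest. The change is advisable and cheap.

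**What to change.** In section 3.6.3:

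- State that discontinuation by the investigator ends study procedures only.
- Remove site PI request as a reason to end observation.
- Continue collecting endpoint data (device interrogations, admissions, vital status) to 24 months unless the subject withdraws consent for it.
- Censor only at withdrawal of consent, true loss to follow-up, or end of follow-up.
- State that death counts as a primary endpoint event, and take it out of the list of censored discontinuations.

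In section 9.3:

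- Report discontinuations by arm and reason.
- Add a tipping-point sensitivity analysis that varies, by arm, how many censored subjects are assumed to have had an event, and reports where the conclusion changes.

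The cost is wording in two sections, continued outcome collection for what should be a few subjects through visits and interrogations already scheduled in section 4.7, and a little more analysis.

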- Patient has been informed of the nature of the study and has agreed to its provisions and provided written informed consent approved by the Institutional Review Board.

Exclusion Criteria:

- Any history of debilitating stroke with neurologic deficit
- ST elevation MI or previous cardiac surgery within 60 days prior to enrollment
- Patient is pregnant or nursing
- Patient has chronic NYHA class IV heart failure
- Patient has incessant VT necessitating immediate treatment
- Patient has VT/VF thought to be from channelopathies
- Limited life expectancy (less than one year)
- Patient has current class IV angina
- Recent CABG or PCI (< 45 days)
- Patient is currently participating in another investigational drug or device study
- Patient is unable or unwilling to cooperate with the study procedures
- Known presence of intracardiac thrombi
- Prosthetic mitral or aortic valve or mitral or aortic valvular heart disease requiring immediate surgical intervention
- Major contraindication to anticoagulation therapy or coagulation disorder
- Left Ventricular Ejection Fraction < 15%
- Patient has had a previous ablation procedure for VT, excluding remote (> 3 months) outflow tract tachycardia
- Patient has GFR < 30 mL/min/1.73m^2
- Patient has peripheral vascular disease that precludes LV access
- Patient is thought to have idiopathic outflow VT as only VT
- Patient has a PVC or VT induced cardiomyopathy that is expected to resolve with ablation and will not require an ICD
- Patient has reversible cause of VT
- Patient does not meet criteria for ICD or CRT-D

Intervention:

[figure not shown]
- 1) ICD with medical management
- 2) ICD with catheter ablation. Main strategy is scar-based ablation with targeting of late potentials defined as low voltage potentials with fractionated, split, or delayed components
- 3) Registry on non-randomized patients undergoing ablation only.

Study Endpoint:

The primary endpoint is defined as a composite of recurrent VT, cardiovascular rehospitalization, and death. Prespecified secondary endpoints include each of the individual components of the primary endpoint. Comparison of the ablation-only registry with the randomized patients will serve as an additional secondary outcome measure.

Length of Study:

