#### **3.2 Study endpoints**

The primary efficacy endpoint is defined as freedom from recurrent VT, cardiovascular rehospitalization, and all-cause mortality through a period of 2 years after the procedure (ablation) or randomization (standard medical therapy). Recurrent VT is defined as any appropriate ICD therapy (shock or ATP) or documented sustained monomorphic VT >30 seconds. Cardiovascular rehospitalization is defined as a hospital admission after the randomized procedure for heart failure, procedure-associated complication, or arrhythmia-related causes during the follow-up period.

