### **9.2 Primary Endpoint**

The primary efficacy endpoint is defined as freedom from recurrent VT, cardiovascular rehospitalization, and all-cause mortality through a period of 2 years after the procedure (ablation) or randomization (standard medical therapy). Recurrent VT is defined as any appropriate ICD therapy (shock or ATP) or documented sustained monomorphic VT >30 seconds. Cardiovascular rehospitalization is defined as a hospital admission after the randomized procedure for heart failure, procedure-associated complication, or arrhythmia-related causes during the follow-up period.

Prespecified secondary endpoints include each of the individual components of the primary endpoint. Comparison of the ablation-only registry with the randomized patients will serve as an additional secondary outcome measure.

Prespecified subgroup analysis will be performed for patients with RV cardiomyopathy.

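### Section 3.6.3 lists death as a discontinuation and censors every discontinued patient, which contradicts the endpoint and analysis sections, where death is an event

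*Combined protocol and SAP*

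**What the plan says.** Section 3.6.3 gives five ways a subject is discontinued: loss to follow-up, request of the subject or family, termination by the investigator, termination by the site's principal investigator, and "Subject Death". One closing rule covers all five: "the data collected from this subject will be used in the final analysis and treated as censored subject".

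Elsewhere death is an outcome:

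- Section 1: "The primary endpoint is defined as a composite of recurrent VT, cardiovascular rehospitalization, and death".
- Section 3.2, repeated in 9.2: the endpoint is "freedom from recurrent VT, cardiovascular rehospitalization, and all-cause mortality" over 2 years.
- Section 9.2: "Prespecified secondary endpoints include each of the individual components of the primary endpoint", so death is also a secondary endpoint by itself.
- Section 9.3: Kaplan-Meier "estimates of the primary endpoint and overall survival will be generated", with confidence intervals for a median time in which death is named as an event.

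On censoring, Section 9.3 says only that the primary analysis will "account for censored observations for all randomized subjects". It does not say who those patients are.

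**The concern.** A patient who dies cannot be both censored and an event in the same analysis. The 3.6.3 rule refers expressly to the final analysis, so it is more than an administrative note. It is also the only text that assigns censored status, and no section exempts death or gives 9.3 precedence. The visit table in Section 4.7 repeats the grouping by placing death and withdrawal in one row.

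What is at stake is the event definition for the primary composite, the death component and overall survival. The annual interim comparisons in 9.3 would presumably use the same definition. Each center enters and monitors its own data (Sections 8, 4.9 and 10), so a single written rule on event versus censored status is needed for consistent coding.

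**Working it through.** **Step 1. The texts applied to one patient.** Take a patient who dies at month 10 with no earlier VT or cardiovascular admission.

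| Analysis | Under 3.2, 9.2 and 9.3 | Under 3.6.3 as written |
|---|---|---|
| Primary composite | event at month 10 | censored at month 10 |
| Death component | event | censored |
| Overall survival | event | censored |
| Recurrent VT alone; cardiovascular rehospitalization alone | not stated | censored |

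The first three rows conflict. With every death censored, overall survival and the death component have zero events. That result needs no assumption. Only in the last row, where death is not the event, is censoring at death a usable rule. That row includes the Section 9.3 item: "The median time to VT recurrence as well as the 95% confidence intervals will be reported for both groups". The plan does not draw this distinction.

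**Step 2. The plan's own figure.** Inputs from Sections 9.1 and 3.5.1: 50% of controls with an event at 2 years, a 50% reduction (so 25% with ablation), N = 120, 1:1 allocation, two-sided alpha 0.05, 80% power.

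- Two proportions, 60 per arm, pooled variance under the null: power 81.6%.
- Constant hazards: HR = ln(0.75)/ln(0.50) = 0.415. Freedman's formula gives 46 events, and 46/0.375 gives N = 123.

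The stated 120 is reproduced closely. The contradiction does not depend on it.

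**Step 3. Baseline for the illustration.** Assume complete 2-year follow-up and constant hazards.

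- Hazards: control ln(2)/2 = 0.3466 per year; ablation -ln(0.75)/2 = 0.1438 per year.
- Expected first events: 60 × 0.50 + 60 × 0.25 = 30 + 15 = 45.
- Schoenfeld power = Φ(√D/2 × |ln HR| − 1.96). With D = 45 and |ln 0.415| = 0.879: Φ(2.95 − 1.96) = 83.9%.

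**Step 4. Same death share s of first events in both arms.** Events left = 45(1 − s), the HR is unchanged, and the control 2-year Kaplan-Meier event estimate is 1 − 0.5^(1 − s).

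| s | Events left | Power | Control 2-year estimate |
|---|---|---|---|
| 0 | 45 | 83.9% | 50% |
| 5% | 42.8 | 82.0% | 48.2% |
| 10% | 40.5 | 79.9% | 46.4% |
| 20% | 36.0 | 75.1% | 42.6% |
| 30% | 31.5 | 69.4% | 38.4% |

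A log-rank simulation (20,000 trials, 60 per arm) gives power 1 to 2 points lower in every row, with the same pattern.

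The range of s is assumed. Section 9.1 mentions about 10% per year for death but does not say how that relates to the 50%. If it is control mortality inside the 50%, independent of the other components, the share is -ln(0.9)/0.3466 = 0.1054/0.3466 = 30%. If death and rehospitalization each add a hazard of 0.10 per year to the 50%, the share is 0.10/(0.3466 + 0.20) = 18%.

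**Step 5. Death share differing by arm.** Hold the composite HR at 0.415 and set the control death share at 10% (hazard 0.03466 per year). Let k be the hazard ratio for death as a first event. With deaths censored, HR = (0.1438 − k × 0.03466)/(0.3466 − 0.03466), and events left = 30 × 0.9 + 15 × (1 − k × 0.03466/0.1438).

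- k = 0.8: HR 0.37, events 27 + 12.1 = 39.1, power about 87%.
- k = 0.2: HR 0.44, events 27 + 14.3 = 41.3, power about 75%.

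If ablation reduces death less than the other components, censoring deaths overstates the benefit and power rises above the baseline. If it reduces death more, benefit is understated and power falls.

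**The case against.** The best defence is that the intention is clear. Section 3.6.3 lists ways that participation ends. The sections that define and analyse the endpoint treat death as an event, and 9.3 names it in the median to be estimated. Section 4.8 lists a death report form and 5.3 collects the date of death. The literal rule also exposes itself: overall survival would be 100% in both arms, and any analyst would notice.

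This stands as to likelihood. A real loss of deaths from the final analysis is improbable, and a reader who infers that the trial will have no mortality result goes further than the documents allow. It does not remove the contradiction, because the text has no exception and no order of precedence.

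Three further inferences are also unsupported:

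- That the rule always costs power. Step 5 shows a case in which power rises.
- That the mortality figure in Section 2.1 (a 7-fold risk after recurrent VT) can narrow the range of death shares. It is an association seen after catheter ablation and cannot simply be applied to controls with an ICD alone.
- That 3.6.3 creates a competing-risk fault in the component analyses. Censoring at death is a valid cause-specific approach there. Cumulative incidence with death as a competing event is a separate, optional addition.

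**Conclusion.** The plan is wrong as written, probably through a drafting slip, and should be corrected before outcomes are analysed, since it concerns what counts as an event in the primary endpoint. The certain part is confined to literal application: no events for overall survival or the death component, and every death that is a first event lost from the composite.

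The size of the effect on the composite is illustrative. It rests on 60 per arm, complete follow-up, constant hazards and an assumed death share. With equal shares of 5 to 30%, power goes from about 84% to between 82% and 69%. With a 10% control share and unequal mortality effects, the hazard ratio shifts from 0.415 to 0.37 or 0.44, and power to about 87% or 75%. None of this shows that the sample size is wrong: once death is counted as an event, the planning figures stand.

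**What to change.** - In 3.6.3, except death from the censoring sentence.
- In 3.6.3 and 9.3, state that death from any cause is an event on its date in the composite (if no component event came earlier), in the death component and in overall survival.
- State that only discontinuations other than death are censored, at the last date the patient was known to be event-free, and that any earlier event is kept.
- State that in the separate analyses of recurrent VT (including its median time) and cardiovascular rehospitalization, a patient who dies without that event is censored at death.

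The cost is a few sentences in two sections. Sample size, stated power, visits and case report forms do not change, and the date of death is already collected.
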